5 STUDY TIMELINES

The study is expected to start during the 1th Quarter of 2015.

The overall duration of the study is three years (1 year of recruitment + 2-year observation period).

Study closure is expected to occur in the 2nd Quarter of 2018.

6 STUDY POPULATION

6.2 INCLUSION CRITERIA

Study subjects must fulfill the following criteria:

1. Patients who signed the informed consent
2. Male or female patients, 18 years or older;
3. Patients with chronic or intermittent, watery diarrhea of unknown etiology for more than 4 weeks
4. Patients who are eligible for complete colonoscopy according to physician's clinical criteria

6.3 EXCLUSION CRITERIA:

Subjects will be excluded if at least one of the following criteria is met:

1. Patients with history of IBDs or any other known intestinal disease.
2. Any condition that precludes the patient to undergo complete colonoscopy.
3. Patients who are being treated with any investigational agent;
4. Pregnancy
5. Patients who are not willing to comply with routine clinical appointments or procedures.

6.4 DISCONTINUATION FROM OBSERVATION PERIOD (MC PATIENTS)

In this study, patients with confirmed diagnosis of MC will be followed up to a maximum period of 24 months. However, observation may be stopped prior to the 24 months for different reasons including, but not limited to:

- Adverse event
- Violation of the study protocol
- Lost to follow up
- Patient withdrawal of consent
- Death

In the case observation period is stopped prior to the 24 months, the date of study discontinuation and the reason for discontinuation should be recorded in the electronic Case Report Form (eCRF).

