3.2 SECONDARY OBJECTIVES

- To determine the prevalence of MC subtypes (CC, LC and IC)
- To compare the socio-demographic, clinical and histological characteristics and previous therapies of patients with confirmed diagnosis of MC (MC patients) versus patients without diagnosis of MC (non-MC patients)
- To describe the therapeutic attitude regarding MC patients over a period of 24 months
- To describe the clinical activity of MC patients over a period of 24 months.
- To describe the histological features of MC patients 24 months after diagnosis.
- To explore the association of socio-demographic, clinical and histological characteristics with clinical activity among MC patients followed for 24 months.
- To explore the association of socio-demographic, clinical characteristics with histological activity among MC patients followed for 24 months.
- To explore the correlation between the treatments used by MC patients and clinical activity.
- To explore the correlation between the treatments used by MC patients and histological activity.

- To explore the correlation between fecal calprotectin, EPC and EPX levels and clinical activity among MC patients.
- To explore the correlation between fecal calprotectin, EPC and EPX levels and histological activity among MC patients.

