4 STUDY DESIGN

This is a multicenter, cross-sectional, observational study aiming to determine the prevalence of MC among a consecutive sample of subjects who attend a specialist consultation with symptoms of chronic watery diarrhea. In addition, the study design contemplates a 24-month prospective component with repeated measures for all patients with confirmed diagnosis of MC.

There is no imposed experimental intervention or treatment in this study. All therapeutic decisions and management of subjects will be done according to routine clinical practice.

All subjects who meet eligibility criteria and give their written informed consent to participate will be consecutively enrolled and characterized regarding several socio-demographic and clinical characteristics of interest. All eligible subjects will undergo a colonoscopy according to the routine practice for this type of population (Figure 1). Colonic specimens from all segments will be collected for subjects with macroscopically normal colonoscopies as part of the differential diagnosis of MC. Subjects with abnormal findings in colonoscopy suggestive of disorders other than MC will not be included in the prospective component of the study. These patients will continue to be managed according to the center's routine procedures.

The subjects with confirmed diagnosis of MC (upon histology assessment) will be followed over a period of 24 months in this study in order to investigate the clinical and histological progression. The data collection time points over this period will reflect this routine schedule. According to previous epidemiological studies on MC, it is estimated that 10-15% of patients with chronic, watery diarrhea will have a confirmed diagnosis of MC.^{23,37}

Patients without confirmed histological diagnosis of MC will not be followed up during the prospective part of the study. These patients will continue to be managed according to the center's routine procedures.

Socio-demographic and clinical characteristics of patients without diagnosis of MC (either based on macroscopic or histological assessment) will be directly compared with MC patients.

Overall, 300 subjects will be included in this study. The recruitment period will last one year but may be extended if the target number of participants is not achieved within the defined timeframe.

A total of 10 centers in Portugal are expected to participate. Subject recruitment will be competitive across participating centers.

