8.2 SECONDARY ENDPOINTS

- Proportion of patients with confirmed diagnosis of each subtype of MC (CC, LC and IC)
- Age, gender, BMI, smoking status, duration of symptoms, stool frequency and consistency (type), familial history of IBDs, comorbidities, previous pharmacological/ non-pharmacological therapies and laboratory parameters to be compared between MC patients and non-MC patients.
- Treatments (pharmacological/non-pharmacological) prescribed by specialist for patients with MC diagnosis
- Number of stools and type (Bristol stool form scale), urgency and abdominal pain over the last 7 days before each time point of assessment for patients with MC diagnosis.
- Proportion of MC patients with clinical remission at each data collection time point (month 3, 6, 9, 12, 15, 18, 21 and 24)
Clinical remission: mean of < 3 stools per day and mean of < 1 watery stool per day
- Proportion of MC patients with histological remission at month 24.
See section 8.3.2 for definition of histological remission
- Age, gender, BMI, smoking status, duration of symptoms, stool frequency and consistency, familial history of IBDs, age at diagnosis of MC, time to diagnosis of MC, comorbidities, pharmacological/non-pharmacological therapies, laboratory parameters and histological features, compared with clinical activity status (active/non active) described for patients with MC diagnosis.
- Age, gender, BMI, smoking status, duration of symptoms, stool frequency and consistency, familial history of IBDs, age at diagnosis of MC, time to diagnosis of MC, comorbidities, pharmacological/non-pharmacological therapies, laboratory parameters, compared with histological features, described for patients with MC diagnosis.
- Area under the ROC curve of fecal calprotectin, ECP and EPX levels with clinical activity at each data collection time points among MC patients.
- Area under the ROC curve of fecal calprotectin ECP and EPX levels with histological activity at each data collection time points among MC patients

For definition of clinical and histological activity see section 8.3.1 and 8.3.2.

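### Section 6.4 lets observation of MC patients end for an adverse event or protocol violation although no treatment is imposed, which permits avoidable and possibly outcome-related loss of follow-up data

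*Protocol*

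**What the plan says.** Section 6.4 of the Protocol applies to patients with confirmed MC in the 24-month prospective part. It states that "observation may be stopped prior to the 24 months for different reasons including, but not limited to" five reasons. The first two are "Adverse event" and "Violation of the study protocol"; the others are loss to follow-up, withdrawal of consent and death. When observation ends early, the site enters the date and the reason in the eCRF. Section 6.4 describes no data collection after that.

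Section 4 says: "There is no imposed experimental intervention or treatment in this study". It leaves all management to routine practice and adds: "The subjects with confirmed diagnosis of MC (upon histology assessment) will be followed over a period of 24 months in this study".

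Section 3.2 includes the objective "To describe the therapeutic attitude regarding MC patients over a period of 24 months". It also includes objectives on clinical activity over the same period, on histology at 24 months, and on the relation of treatments and faecal markers to both kinds of activity. Section 8.2 reports clinical remission as a proportion at each three-monthly time point and histological remission as a proportion at Month 24. Section 9.1 summarises these with 95% confidence intervals. Neither section says how a patient whose observation has ended enters the denominator.

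**The concern.** In a trial of a study drug, an adverse event can end treatment, and some protocols end follow-up at the same time. Here there is no study drug to withdraw. A patient who has an adverse event, or departs from the protocol, still attends routine appointments that can be recorded. Consent withdrawal, loss to follow-up and death do stop recording; these two events by themselves do not.

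The rule also works against the protocol's own data plan. Section 7.1 collects concomitant medications and worsening or new illness at every follow-up time point, and the Appendix schedules the therapeutic attitude from Month 3 to Month 24. An illness that section 7.1 treats as data could, under section 6.4, be the reason the record closes. Section 6.4 gives no definition or threshold for either reason and leaves the list open, so each site decides for itself.

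At stake are the remission proportions, the description of therapy over 24 months, and the analyses of treatments and faecal markers against activity.

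**Working it through.** **The plan's own figures (section 9.2).** With 300 patients the 95% half-width is 1.96 × √(p(1−p)/300). This gives 3.39 points at p = 10% and 4.04 points at p = 15%, both below the stated 4.5. The expected MC cohort at 10% is 300 × 0.10 = 30. Both figures reproduce. Section 6.4 does not touch them, because prevalence is settled at baseline.

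**Weight of one patient.** 1/30 = 3.3% of the cohort.

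**Shift in a remission proportion.** Let d be the share of the cohort stopped, p_r remission among those retained, and p_s remission that the stopped patients would have shown. If stopped patients leave the denominator:

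- reported proportion = p_r
- full-cohort proportion = (1 − d) × p_r + d × p_s
- shift = d × (p_r − p_s)

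The protocol gives no value for d, p_r or p_s. Assume 30 MC patients and p_r = 60%, and let the rest vary. Shift in percentage points (plus means overstated):

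| Stopped | p_s = 0% | 30% | 60% | 90% | 100% |
|---|---|---|---|---|---|
| 3 (10%) | +6 | +3 | 0 | −3 | −4 |
| 6 (20%) | +12 | +6 | 0 | −6 | −8 |
| 9 (30%) | +18 | +9 | 0 | −9 | −12 |

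For six stopped and p_s = 0%, the full-cohort value is 24 × 0.60/30 = 48% against 60% reported. For p_s = 100% it is (14.4 + 6)/30 = 68%.

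With six stopped, the range is +10 to −10 points at p_r = 50% and +14 to −6 points at p_r = 70%.

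**A different denominator.** If stopped patients are instead counted as not in remission, six stopped give 14.4/30 = 48% reported. That is right if none would be in remission and 68 − 48 = 20 points too low if all would be. This choice rules out overstatement but not bias.

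**Against sampling error.** At 60% the 95% half-width is 1.96 × √(0.24/30) = 17.5 points with 30 patients and 1.96 × √(0.24/24) = 19.6 points with 24. In the six-patient case the largest shift, 12 points, is about two thirds of the half-width, and the interval does not reflect it.

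**The case against.** The strongest case on the other side has five parts.

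1. **Stopping is permitted, not required.** A reader might infer that patients who tolerate treatment badly will drop out and that remission is therefore overstated. The documents do not support this. Section 6.4 does not tie an adverse event to MC treatment; it could be any intercurrent illness. A protocol violation has no stated link to remission. This stands: the direction is not fixed.

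2. **The denominator is not stated.** Overstatement needs stopped patients to leave the denominator and also to do worse than those retained. How they are counted is commonly left to a statistical analysis plan, which may exist but is not shown. This stands for the remission proportions. No analysis plan, however, can recover symptoms, therapy changes, faecal markers or histology that were never collected.

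3. **Missed diaries are already handled.** A reader might take a missed diary as a violation that closes the record. Section 7.2 has the counts estimated and flagged when a diary is forgotten or lost. With fewer than five days of entries and no further information, that week is not evaluable. This stands, and a missed diary is not an example of the problem.

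4. **The design expects poor courses to be followed.** Section 7.1 and the Appendix plan for treatment changes, and data collected before stopping remain usable. That is true, but it shows section 6.4 to be out of step with the rest of the protocol and does not neutralise it.

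5. **Only secondary analyses are affected.** The protocol predefines no hypothesis and the primary endpoint is untouched. This stands and limits the weight of the point.

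**Conclusion.** The point holds as a fault in the data-collection rule. Section 6.4 allows follow-up to end for two reasons that do not by themselves prevent recording in a study that imposes no treatment, and it does so in an open list. The resulting loss is avoidable and may be related to outcome. It may bias the secondary remission proportions and the treatment-activity analyses, plausibly upward for remission if patients doing poorly are the ones stopped.

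It would go too far to say that remission is overstated. Direction and size depend on who is stopped and on the denominator, and the protocol fixes neither. The range of +12 to −8 points rests on assumptions that are not in the documents: six of 30 patients stopped, 60% remission among those retained, and stopped patients left out of the denominator. The change is worth making because the cohort is small and the loss cannot be repaired at analysis.

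**What to change.** In section 6.4:

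- Remove adverse event and protocol violation as reasons to end observation.
- Replace the open list with a closed one: withdrawal of consent, loss to follow-up, death, and premature termination of the study. The last is needed for consistency with section 10.3.
- State that an adverse event or protocol deviation is recorded in the eCRF, and that available routine-care data continue to be collected to Month 24.
- State that this rule requires no study procedure of an individual patient, including the Month 24 colonoscopy, which remains a clinical decision.

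The cost is a change of protocol wording, an eCRF entry for the event, and continued data entry for a few patients. Medication and illness changes are already collected at each time point. The sample size and the primary analysis do not change.

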7 INFORMATION TO BE COLLECTED

7.1 VARIABLES TO BE CAPTURED

Baseline characteristics

The following socio-demographic, clinical characteristics will be collected for all eligible subjects.

- Date of birth
- Sex
- Height
- Weight
- Smoking status
 - non-smoker: never smoked before or smoked a little occasionally
 - former smoker: patients who had quit smoking more than 6 months before inclusion in the study;
 - current smoker: greater than 7 cigarettes (or approximately half a pack) per week for at least 6 months and had reported any cigarette smoking in the previous 6 months.
- History of bowel surgery
- Familial history of IBDs
- Date of start of first symptoms of diarrhea (at least the month and the year when the patient first experienced non-bloody, watery diarrhea)
- Acute onset of symptoms (yes/no)
- Symptoms (to be captured by the physician by interviewing the patient and referring to the previous 7 days):
 - number of stools per day (the mean number of stools and watery stools per day will be calculated by summing the number of stools [any type] and watery stool that occurred over the week before the time point of assessment divided by 7 days).
 - type of stool (1 to 7 - Bristol Stool Chart)
 - nightly diarrhea
 - urgency (0 = no urgency, 1 = need to defecate within 30 minutes, 2=immediate need to empty the bowel, 3 = fecal incontinence - have to go immediately to the toilette)
 - difficulties staying continent with a respective bowel movement
 - abdominal pain (0 = no pain, 1 = mild, 2 = moderate, 3 = severe pain)
- Unexplained weight loss (> 4.5 kg) in the previous 6 months.
- Comorbidities, including the following conditions of interest: heart disease, hypertension, malignant disease, bile acid malabsorption, celiac disease, rheumatoid arthritis, Diabetes mellitus I, Sjögren's syndrome, Raynaud's syndrome, psoriasis, thyroiditis, hyperthyroidism, hypothyroidism, other auto-immune disorders.
- Pharmacological therapies (within the previous 3 months before study inclusion), including the following therapies of interest: NSAIDs, salicylic acid, proton pump inhibitors, SSRIs and statins.
- Laboratory parameters (prior to colonoscopy) - hemoglobin, platelets, leukocytes, neutrophils, eosinophiles, basophiles, monocytes, lymphocytes, erythrocyte sedimentation rate (ESR), C-reactive protein (CRP), iron and transferrin.
- Fecal sample - for assessment of calprotectin, ECP and EPX levels.
- Result of colonoscopy: normal/abnormal - describe whether other findings may have caused diarrhoea (e.g., polyps > 2 cm, tumors, Crohn's disease, ulcerative colitis, ischemic colitis, other).

For patients with macroscopically normal colonoscopy:

- Date of sampling of colonic specimens (this date will correspond to the date of MC diagnosis, if confirmed).
- Date of histological assessment
- Histological evidence of MC (yes/no). The following features will be captured:
 - Geboes Index (grade for each of the colon segments: rectum, sigmoid, descending, transverse and ascending) – see Section 7.4.2.
 - Thickness of the subepithelial collagen layer (not observed, $\leq 5 \mu\text{m}$; > 5 and $< 10 \mu\text{m}$; $\geq 10 \mu\text{m}$)
 - IEL in the surface epithelium (not observed, < 5 IEL/100 surface epithelial cells, > 5 and < 20 IEL/100 surface epithelial cells, ≥ 20 IEL/100 surface epithelial cells);
- If a diagnosis of MC was not confirmed, was other diagnosis established? Yes/no - if yes, describe.

Characterization of MC patients

- MC histological assessment: location of microscopic findings (by colon segment), type of MC (lymphocytic, collagenous, incomplete colitis) - see histological assessment in section 7.4.
- Therapeutic attitude upon MC confirmation
 - Antidiarrheal medication (e.g., loperamide or diphenoxylate/atropine),
 - Bismuth subsalicylate or aminosalicylates, e.g. 5-aminosalicylic acid
 - Cholestyramine
 - Corticosteroids (budesonide, prednisolone)
 - Immunosuppressive agents, e.g. azathioprine, 6-mercaptopurine or methotrexate
 - Surgical intervention (e.g. ileostomy)
 - Other interventions (pharmacological or non-pharmacological)
- Dispensing of patient diary card to document the number of stools including the type according to Bristol stool form scale (see section 7.2) in the week prior to the next appointment. In addition, the use of additional pharmacological or other therapies will be recorded by the patient.

Follow up assessments of MC patients (as per routine practice) - month 3, 6, 9, 12, 15, 18, 21 and 24.

The following will be assessed throughout the 24-month prospective component of the study - see **Appendix**.

At every data collection time point

- Weight (kg)
- Symptoms (to be captured by the physician by checking the patient diary and interviewing the patient, referring to the previous 7 days):
 - number of stools per day (the mean number of stools and watery stools per day will be calculated by summing the number of stools [any type] and watery stool that occurred over the week before the time point of assessment divided by 7 days).
 - type of stool (1 to 7 - Bristol Stool Chart)
 - nightly diarrhea
 - urgency (0 = no urgency, 1 = need to defecate within 30 minutes, 2=immediate need to empty the bowel, 3 = fecal incontinence - have to go immediately to the toilette)

- difficulties staying continent with a respective bowel movement
- abdominal pain (0 = no pain, 1 = mild, 2 = moderate, 3 = severe pain)
- Laboratory parameters – hemoglobin, platelets, leukocytes, neutrophils, eosinophiles, basophiles, monocytes, lymphocytes, erythrocyte sedimentation rate (ESR), C-reactive protein (CRP), iron and transferrin.
- Concomitant medications
- Changes in concomitant illness (worsening of previous conditions, new condition)

At diagnosis of MC and every 3 months up to month 24:

- Fecal sample – for assessment of calprotectin, ECP and EPX levels.

In addition, at Month 24 only:

- Date of colonoscopy with sampling of colonic specimens
- Result of colonoscopy: normal/abnormal - describe
- Date and result of histological assessment :
 - Geboes Index (grade for each of the colon segments: rectum, sigmoid, descending, transverse and ascending) – see Section 7.4.2.
 - IEL in the surface epithelium (not observed, < 5 IEL/100 surface epithelial cells, > 5 and < 20 IEL/100 surface epithelial cells, ≥20 IEL/100);
 - Thickness of the subepithelial collagen layer (not observed, <5 µm; > 5 and < 10 µm; ≥ 10 µm).

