2 INTRODUCTION

2.1 MICROSCOPIC COLITIS

Microscopic colitis (MC) is a chronic inflammatory bowel disease, characterized by watery, non-bloody diarrhea with macroscopically normal colonic mucosa and typical microscopic features. Other clinical findings of MC may include nocturnal diarrhea, faecal incontinence, abdominal pain and mild weight loss.^{1,2}

No unifying mechanism has been identified as being responsible for the pathophysiological abnormalities found in MC and the disease is likely to have multifactorial causes.³ Several risk factors such as cigarette smoking, especially among young patients,⁴ have been shown to be associated with the increased incidence of the disease. Diversion of the fecal stream has sometimes resulted in histological improvements,⁵ suggesting that the disease is caused by an abnormal response to luminal antigens. A wide variety of drugs have been proposed as potential triggers or etiological factors for MC, but none has been conclusively implicated. These include the non-steroidal anti-inflammatory drugs (NSAIDs), proton pump inhibitors (PPIs), selective serotonin reuptake inhibitors (SSRIs) and statins. However, all these drugs are widely used, therefore, it is expected that patients with MC might frequently use them coincidentally. Some authors point out that drug-induced MC cases are more likely due to an idiosyncratic reaction.^{6,7}

The diagnosis of MC rests on characteristic pathological findings in biopsies from normal or oedematous colonic mucosa. Although the topographic distribution of MC remains controversial, rectal biopsies are not sufficient.^{6,8} Some studies demonstrate that biopsies from the right and transverse colon are necessary for the diagnosis of MC, while others demonstrate that biopsies from the descending and sigmoid colon suffice for diagnosing this disease.⁸⁻¹² However, colonoscopy should be preferred because it is essential to rule out malignant colonic disease. Diarrhea caused by other diseases should be excluded; these diseases include bile acid diarrhea, coeliac disease, and lactose malabsorption.¹³

Two distinct histological types of MC, lymphocytic colitis (LC) and collagenous colitis (CC), have been described, but overlapping features are often present; indeed, some authors think that LC and CC are two histological subtypes of the same disease.^{3,14}

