9.2 SAMPLE SIZE

This study will include 300 patients with chronic diarrhea allowing the estimation of a prevalence of 10-15%^{23,37} with an error margin of less than 4.5% and with 95% confidence interval. Assuming the lowest rate of the prevalence interval (10%), approximately 30 patients with MC are expected to be followed in the prospective component study.

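### The three smoking-status categories in 7.1 leave gaps and overlap, so a variable used in three secondary comparisons is open to misclassification and inconsistent coding

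*Protocol*

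**What the plan says.** Section 7.1 (baseline characteristics) gives three smoking categories:

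- "non-smoker: never smoked before or smoked a little occasionally". No amount or time limit is attached, and the patient need not have stopped.
- "former smoker: patients who had quit smoking more than 6 months before inclusion in the study". No minimum past consumption is required.
- For current smoking the text requires "greater than 7 cigarettes (or approximately half a pack) per week for at least 6 months and had reported any cigarette smoking in the previous" six months. All three conditions (rate, duration, recent smoking) must hold.

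There is no residual category, and no other section settles borderline cases. Section 7.1 lists no cigarettes per week, start date or quit date. The appendix schedule collects smoking status once, at baseline.

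Section 2.1 treats smoking as relevant to the disease: "Several risk factors such as cigarette smoking, especially among young patients" are reported as associated with higher incidence. Section 8.2 lists it among the variables to be compared ("Age, gender, BMI, smoking status, duration of symptoms, stool frequency and consistency (type), familial history of IBDs", ending with "laboratory parameters to be compared between MC patients and non-MC patients"). It appears again in the comparisons by clinical activity and by histological features.

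**The concern.** A categorical exposure is usable only if each patient fits exactly one category. Here some patients fit none, some fit two, and some who still smoke belong by definition with people who never smoked. Section 4 expects 10 centres, and each would have to decide alone what light occasional smoking means and where to put patients who fit nowhere. Borderline coding could then vary by site.

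This is a data-capture rule, so an analysis plan cannot repair it. If only the category is recorded, the data listed in the protocol give an analyst nothing from which to recover true status. At stake is the reliability of smoking status in the three secondary comparisons of 8.2, for a factor that the protocol's introduction singles out.

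**Working it through.** **The plan's own figure.** The only sample-size figure is in section 9.2: "This study will include 300 patients with chronic diarrhea allowing the estimation of a prevalence of 10-15"% with a margin below 4.5%. The Wald half-width is 1.96 × √(p(1 − p)/300). It is 3.39% at p = 0.10 and 4.04% at p = 0.15, so the statement reproduces. It does not involve smoking and is not affected by this point.

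**Applying the three definitions literally.** Non-smoker: never smoked, or only light occasional smoking. Former: stopped more than 6 months before inclusion. Current: more than 7 a week, and for at least 6 months, and any smoking in the last 6 months.

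| Profile | Category reached |
|---|---|
| Never smoked | Non-smoker |
| 20 a day for years, continuing | Current |
| 20 a day for years, stopped 3 months ago | Current |
| 20 a day for years, stopped more than 6 months ago | Former |
| 20 a day, started 3 months ago | None: fails the 6-month duration; not former; not light or occasional |
| One a day (7 a week) for years, continuing | None clearly: not above 7; not former; regular, not occasional |
| One a day, stopped 3 months ago | None clearly: not above 7; stopped too recently for former |
| Light occasional smoker, stopped more than 6 months ago | Non-smoker and former |
| Light occasional smoker, continuing | Non-smoker only |

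The definitions therefore have gaps and one overlap, and they place some continuing smokers in the unexposed group. Current and former do not overlap.

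**The two cut-offs.** More than 7 cigarettes and half a pack agree only for a pack of about 14 (2 × 7). If a pack holds 20, an assumption, half a pack is 10, and a smoker of 8 or 9 a week passes one cut-off but not the other.

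**Illustrative size.** The protocol gives no smoking distribution, so every smoking figure below is assumed. Group sizes follow section 9.2: 300 × 0.10 = 30 MC and 270 non-MC.

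Take true current smoking of 35% in MC and 20% in non-MC, with a share f of smokers recorded as non-smokers equally in both groups. The observed odds ratio is [0.35(1 − f) / (1 − 0.35(1 − f))] ÷ [0.20(1 − f) / (1 − 0.20(1 − f))].

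- f = 0: (0.35/0.65) ÷ (0.20/0.80) = 2.15
- f = 0.1: (0.315/0.685) ÷ (0.18/0.82) = 2.09
- f = 0.2: (0.28/0.72) ÷ (0.16/0.84) = 2.04
- f = 0.3: (0.245/0.755) ÷ (0.14/0.86) = 1.99

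For scale, the standard error of the log odds ratio at f = 0 is √(1/10.5 + 1/19.5 + 1/54 + 1/216) = 0.412. The 95% interval is therefore about 0.96 to 4.83.

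A second illustration assumes a true odds ratio of 2.5 with 20% smoking in non-MC, and a two-sided 5% test of two proportions (normal approximation). Power is 62% with no misfiling. At f = 0.1, 0.2 and 0.3 it is 57%, 52% and 47%, and the observed odds ratio is 2.41, 2.33 and 2.26. The protocol plans no power for this comparison.

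**The case against.** The best defence is that the rule works for most patients and that the rest is of little consequence. A minimum consumption for current smoking is a legitimate definition, so placing people below it outside that group is not in itself an error. Having quit can be read as presupposing that one was a smoker, which would send the occasional ex-smoker to non-smoker and remove the overlap. A site could likewise put the one-a-day smoker in non-smoker as the only box left. The half-pack remark is marked as approximate. Smoking is one of many covariates in secondary comparisons with no predefined hypothesis, and an odds-ratio shift of 0.06 to 0.16 is minor beside an interval of 0.96 to 4.83. The argument that moving one or two patients changes the result applies to any binary covariate with about 30 MC patients; it reflects the sample size, not this rule.

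Much of this stands. It limits the importance of the point and makes the exact cut-off a matter of choice. It does not close the gap for the recent heavy smoker. The favourable readings are also ones that each site would have to supply, because the text does not state them.

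A reader might also infer that misfiling falls mainly on MC patients, for instance because symptoms led them to cut down, and so erodes the association much further. The documents do not support that. Every enrolled patient has chronic watery diarrhea. One rule is applied to all of them at baseline, and MC is confirmed by later central histology. The current-smoker rule also does not require the rate above 7 a week to be the present rate, so an established smoker who recently cut down can still be coded as current.

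**Conclusion.** The point holds as a defect in a stated definition. The categories are neither exhaustive nor mutually exclusive, they can file continuing occasional smokers as non-smokers, and the current-smoker line carries two cut-offs. Smoking status is therefore open to misclassification and to inconsistent coding across sites, and it cannot be recovered from the data the protocol lists.

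A reader might go further and say that the MC versus non-MC comparison is misclassified. That cannot be shown: without a smoking distribution, the number of patients affected is unknown.

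Error is most likely similar in MC and non-MC patients and would then modestly dilute a smoker versus non-smoker contrast. With three categories the direction is not guaranteed. The shift from 2.15 to between 2.09 and 1.99 rests wholly on the assumed smoking rates and the assumed 10% to 30% misfiling. The primary prevalence estimate is untouched. This is a worthwhile, low-cost improvement to secondary comparisons, not a threat to the main result.

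**What to change.** In section 7.1 and the eCRF, capture the facts behind the category:

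- ever or never smoked;
- any smoking in the 6 months before inclusion;
- usual cigarettes per week;
- smoking duration, or start and quit dates.

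Derive the status from these by a rule in which every patient fits exactly one category. One example is never; former (smoked before, none in the last 6 months); and current (any smoking in the last 6 months). Another consumption threshold would serve as well, provided it is numeric and leaves no gap. Keep the class above 7 a week for at least 6 months as a derivable subgroup. Delete the half-pack parenthesis so that one numeric cut-off remains.

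The cost is three reworded lines and a few extra baseline fields. The downside is that, under the example, the main current-smoker category no longer matches the present definition of more than 7 a week directly, and people who smoke very little count as current. The subgroup preserves the former comparison.
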